9.2.2. Damage Score

The Damage Score (DS) is calculated as a sum of the total poilkiloderma score (POLS), total calcinosis score (CALS) and Gotorn's hands damage score (GHDS).

$$DS = POLS + CALS + GDHS$$

The polikiolderma score characterizes specific dispigmentation in the particulal area and calcinosis score characterizes calcification of the skin in the particular area. The total polikiolderma score (POLS) and the total calcinosis score (CALS) are summed up over 15 individual areas in the body and each of them has range 0-15. The Gotorn's hands damage score (GHDS) has the range 0-2 so that the damage score (DS) has the range 0-32.

In our analysis we will look at the activity score (AS), damage score (DS).

For the activity score we will analyze the following subscores: total extent score (ES), total erythema score (ER), total scaling (SC) and total erosion/ulceration scores (EU), Gottorn hands score (GHS), peringual score (PS), and alopecia score (AS).

For the damage score we will analyze the following subscores: total poilkiloderma score (POLS), total calcinosis score (CALS) and Gotorn's hands damage score (GHDS).

9.3. Additional Information for Safety Endpoints

9.3.1. Adverse Events

An adverse event (AE) is considered treatment emergent relative to a given treatment if:

- the event occurs for the first time during the effective duration of treatment and was not seen prior to the start of treatment (for example, during the baseline or run-in period), or
- the event was seen prior to the start of treatment but increased in severity during treatment.

9.3.2. Laboratory Data

The description of the laboratory data is given in Section 7.8 of the protocol.

9.3.3. Vital Signs

Vital signs (blood pressure, pulse, respiratory rates and temperature) will be measured after 5 minutes of rest as indicated in the Schedule of Activities. Baseline will be the last measurement prior to receiving study treatment.

9.3.4. Electrocardiogram

Single 12-lead ECGs should be collected at times specified in the Schedule of Activities.

The screening ECG values will serve as each subject's baseline values. To ensure safety of the subjects, a qualified individual (investigator or sub-investigator) at the investigator site will make comparisons to baseline measurements. A paper or digital copy of the ECG should be filed in the subject's chart and must be available to the sponsor upon request. Any clinically significant changes will be recorded as AEs and evaluated further, as clinically warranted. In some cases, it may be appropriate to repeat abnormal ECGs to rule out improper lead placement as contributing to the ECG abnormality.

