7.5.2. Electrocardiogram

Single 12-lead ECGs should be collected at times specified in the Schedule of Activities.

All scheduled ECGs should be performed after the participant has rested quietly for at least 10 minutes in a supine position and prior to any blood collection procedures.

The Day 1 pre- dose ECG values will serve as each participant's baseline values. To ensure safety of the participants, a qualified individual (investigator or sub-investigator) at the investigator site will make comparisons to baseline measurements. A paper or digital copy of the ECG should be filed in the participant's chart and must be available to the sponsor upon request. Any clinically significant changes will be recorded as AEs and evaluated further, as clinically warranted. In some cases, it may be appropriate to repeat abnormal ECGs to rule out improper lead placement as contributing to the ECG abnormality.

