9.4.2. Electrocardiogram

Changes from baseline for the ECG parameters (QT interval, heart rate, corrected QT interval QTc (QTcB and QTcF versions) and QRS interval will be summarized by treatment and time. The Day 1 pre-dose ECG measurements will be used as a participant's baseline. The number (%) of participants with maximum post dose QTc values (QTcB or QTcF) and maximum increases from baseline in the following categories will be tabulated by treatment:

	Borderline (msec)	Prolonged (msec)
Absolute Value	≥ 450 - <480	≥480
Absolute Change	30-<60	≥60

In addition, the number of participants with absolute QTc values \geq 500 msec will be listed.

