3. ENDPOINTS AND BASELINE VARIABLES: DEFINITIONS AND CONVENTIONS

In Stage 1, Stage 2, and Amended Stage 2, the primary and secondary endpoints assess changes in the modified CDASI *activity* and *damage* scores. The details of the calculation of these scores are presented in Section 9.2. In Stage 3, the secondary endpoints assess changes in the modified CDASI activity and damage scores *and* changes in the TIS and the components of the TIS. The details of the calculation of the TIS are presented in Section 9.8. In each stage, baseline is defined as the measurement at Day 1 (prior to dosing). Change from baseline is defined as the value at a specific visit minus the value from baseline.

Efficacy endpoint analyses may use data from a single stage or pool data across multiple stages. Stage 1 analyses will include Stage 1 data only, and Stage 3 analyses will include Stage 3 data only. Pooled analyses of data from Stage 1, Stage 2, and Amended Stage 2 will pool data from the first 12 weeks of these stages. For CCI endpoints newly added to Amended Stage 2 that were not previously included in Stage 1 or Stage 2, analyses will occur among Amended Stage 2 participants only.

Primary analysis of the CDASI activity score in Stage 1, Stage 2, and Amended Stage 2 include data from baseline to Week 12. Sensitivity and supportive analyses in these stages may include data beyond Week 12.

Secondary analysis of the TIS, components of the TIS, CDASI activity, and CDASI damage scores in Stage 3 include data from baseline to Week 12. Sensitivity and supportive analyses in these stages may include data beyond Week 12.

3.1. Endpoints in Stage 1

3.1.1. Primary Endpoint in Stage 1

• Change from baseline in CDASI activity score at Week 12.

3.1.2. Secondary Endpoint(s) in Stage 1

- Absolute values and change from baseline of CDASI activity and CDASI damage scores at all scheduled time points. Exception: The change from baseline in CDASI activity score at Week 12 is a primary endpoint.
- Incidence of adverse events (AEs), laboratory abnormalities, changes in vital signs, and electrocardiogram (ECG) findings. The extended discussion of these endpoints is presented in Section 9.3.

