3.6. Baseline Variables

The day 1 measurements will serve as the baseline for clinical reported outcomes (CDASI Scores, Physician Global Assesment Score), patient-reported outcomes (SF36, DLQI, 5D Itch Scale), medical assessments (skin biopsies, ECG, weight, vital signs), laboratory safety measurements

Demographics and medical history data will be collected at the baseline.

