6.7.4. Electrocardiogram

The following ECG data will be listed: QT, QTc (Fridericia's), heart rate, QRS duration, PR interval. QTc based on Fridericia's correction will be derived.

Baseline and change from baseline for QT, QTcF, heart rate, QRS, PR will be summarized using descriptive statistics by treatment and study week in (a) Stage 1, (b) Stage 1, Stage 2, and Amended Stage 2, and (c) Stage 3. For QTcF a classification of absolute values and increase from baseline will be used.

The numbers of subjects with ECG outcomes within the specified categories (see Section 9.7) and number of subjects with uncorrected QT values \geq 500 ms will be summarized by treatment and study week.

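### SAP 9.3.4 makes the screening ECG the baseline, while SAP 3, SAP 3.6 and the protocol use Day 1, so ECG change summaries could be run from the wrong recording

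*SAP*

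**What the plan says.** One statement names screening:

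- SAP 9.3.4: "The screening ECG values will serve as each subject's baseline values".

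Four name Day 1:

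- SAP 3: "In each stage, baseline is defined as the measurement at Day 1 (prior to dosing").
- SAP 3.6: "The day 1 measurements will serve as the baseline for clinical reported outcomes". The same sentence goes on to list "medical assessments (skin biopsies, ECG, weight, vital signs"), so ECG is explicitly included.
- Protocol 7.5.2: "The Day 1 pre- dose ECG values will serve as each participant's baseline values".
- Protocol 9.4.2, the analysis section: "The Day 1 pre-dose ECG measurements will be used as a participant's baseline".

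The outputs that depend on the choice are in SAP 6.7.4 and SAP 9.7. SAP 6.7.4 calls for change from baseline in QT, QTcF, heart rate, QRS and PR, and adds: "For QTcF a classification of absolute values and increase from baseline will be used". SAP 9.7 gives the classes: QTcF increases of 30 to below 60 msec and of 60 msec or more, and percentage increases for PR and QRS. Neither section says which ECG is the baseline.

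**The concern.** The SAP contradicts itself and the protocol on a definition that feeds a safety endpoint. ECG findings are part of the primary endpoint in Stage 3 and a secondary endpoint in the skin stages. For each stage, the SAP endpoint definitions send the reader to SAP 9.3 for further detail on these endpoints, and that is where the outlying sentence sits. Nothing in the SAP ranks 9.3.4 below 3.6.

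A programmer working from the ECG-specific section would use an ECG taken up to five weeks before the first dose. One working from SAP 3.6 would use Day 1. If this is still open at unblinding, the choice between two baselines for a safety table could be made with treatment known.

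**Working it through.** The plan states no figure to reproduce. The check is first textual. An illustration of size follows, on an assumed variability.

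**1. Are these two different recordings?** Yes. All three Schedules of Activities list an ECG at screening and another on Day 1. SAP 9.1 places screening 1 to 35 days before Day 1.

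**2. Could the change be deliberate?** SAP 2 allows the SAP to modify protocol plans, but that cannot reconcile 9.3.4 with SAP 3 and 3.6. The SAP's amendment table (SAP 1) lists no change of ECG baseline. Apart from the baseline it names and minor wording, the 9.3.4 paragraph follows protocol 7.5.2 closely. The screening ECG has its own purpose: exclusion criterion 25 uses it for eligibility.

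**3. Which outputs depend on the choice?**

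| Output | Depends on ECG baseline? |
|---|---|
| Change from baseline in QT, QTcF, heart rate, QRS, PR (SAP 6.7.4) | Yes |
| QTcF increase of 30 to <60 or ≥60 msec (SAP 9.7) | Yes |
| PR and QRS percentage-increase classes (SAP 9.7) | Yes, twice: baseline sets both the applicable threshold (25% or 50%) and the percentage itself |
| Absolute QTcF, PR and QRS classes | No |
| Vital signs | No; they have their own rule in SAP 9.3.3 |
| CDASI and TIS analyses | No |

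**4. How many participants could change QTcF class?** The documents give no within-subject QTcF SD, so it is assumed. The model takes independent normal values at every visit with a common SD and no drug effect. Let S be the screening value, B the Day 1 value and M the maximum of k post-dose values. Each participant is classed at 30 and 60 msec by M − S and again by M − B, and the share with different classes is counted over 500,000 draws. From the schedules, k = 4 in Stage 1 and original Stage 2 (Weeks 4, 8, 12, 28), and k = 7 in Amended Stage 2 and Stage 3 (Weeks 4, 8, 12, 16, 20, 24, 40).

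| Assumed SD (msec) | SD of S − B = SD × √2 | Class differs, k = 4 | Class differs, k = 7 |
|---|---|---|---|
| 8 | 11.3 | 2.6% | 4.0% |
| 10 | 14.1 | 8.9% | 13.0% |
| 12 | 17.0 | 16.8% | 23.3% |
| 15 | 21.2 | 27.7% | 35.3% |

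For SD 8 to 12 the range is about 3% to 23%. Applied to the roughly 76 participants planned overall, the extremes are 76 × 0.0256 = 1.9 and 76 × 0.2327 = 17.7. The upper figure treats everyone as having seven ECG visits, which the 32 Stage 1 participants do not. For Stage 3 alone (8 to 16 participants, k = 7) the range is 8 × 0.0398 = 0.3 to 16 × 0.2327 = 3.7 participants. One participant there is 1/16 = 6% to 1/8 = 13% of the cohort.

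**5. What this does not show.** In this model S and B have the same distribution, so the expected proportion in each class is the same under either baseline. The percentages measure how many individuals are classed differently, not a bias in the rate. A systematic shift would need screening and Day 1 values to differ on average, and the documents give no information on that.

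**The case against.** The strongest reply is that the intent is not in doubt. Four statements say Day 1, including the SAP's general definition and the one section that lists baseline variables. SAP 9.3.4 is an appendix of supplementary information, and its paragraph is largely about site handling of tracings. SAP 6.7.4 and 9.7 never mention screening. Most programmers would probably use Day 1. This stands, and it makes the point an inconsistency to correct rather than a flawed choice of analysis. It does not remove the contradiction, because the endpoint definitions do refer to SAP 9.3.

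The consequence is also limited. SAP 5.1.3 tests no hypotheses in Stage 3, SAP 6.7.1 describes safety analysis as generally exploratory, and no stated decision rule uses the ECG change classes. This stands too.

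A reader might infer a larger effect for a participant near a threshold. For someone 20 msec above Day 1, one could take the chance of being classed at 30 msec or more from screening as 1 − Φ(10/(SD × √2)), which is 19%, 24% and 28% for SD 8, 10 and 12. That treats the gap between screening and Day 1 as unrelated to the observed rise, but both contain the Day 1 value. Take one post-dose ECG and the same independence assumption. Given an observed rise of 20 msec and no drug effect, S − B has mean +10 and SD equal to SD × √1.5. The chance is then Φ(−20/(SD × √1.5)) = 2.1%, 5.1% and 8.7%. If the whole 20 msec is a true effect, the mean is 0 and the chance is Φ(−10/(SD × √1.5)) = 15%, 21% and 25%. The 19% to 28% range should not be used.

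**Conclusion.** The contradiction is real and rests on the text alone. SAP 9.3.4 conflicts with SAP 3, SAP 3.6 and protocol 7.5.2 and 9.4.2, and no recorded amendment explains it. As written, 9.3.4 would base every ECG change summary and the QTcF, PR and QRS increase classes on a recording made 1 to 35 days before Day 1.

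The reach is narrow: descriptive safety tables only, with absolute ECG classes and efficacy results untouched. The 3% to 23% range for participants changing QTcF class depends wholly on the assumed SD of 8 to 12 msec, independent visits and no drug effect. It illustrates that the tables can change and does not predict by how much.

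A reader might infer that the sponsor has chosen the screening baseline, or that the ECG tables will be wrong. The documents support neither. They show only that two instructions conflict and that the sections using the baseline do not settle which applies.

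**What to change.** In SAP 9.3.4, name the Day 1 pre-dose ECG in place of the screening ECG. A cross-reference to SAP 3.6 in SAP 6.7.4 and 9.7 would remove any remaining doubt. Optionally, state that the last pre-dose ECG is used if the Day 1 recording is missing, in line with SAP 9.3.3, which takes the last measurement before treatment for vital signs. Neither document has such a rule for ECG, and the correction does not depend on one. The cost is one SAP sentence, or two with the fallback, made before unblinding. No new data and no change to visits are needed.

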9.4. Patient-Reported Outcomes and physician's Evaluation of Disease

9.4.1. SF36: The Short Form Health Survey

The SF-36 v.2 (Acute version) is a 36-item generic health status measure. It measures 8 general health concepts or domains: physical functioning (PF), role physical (RP), bodily pain (BP), general health (GH), vitality (VT), social functioning (SF), role emotional (RE) and mental health (MH). These domains are also summarized as physical and mental component scores (PCS and MCS). All domains and summary components are scored such that a higher score indicates a higher functioning or health level.

9.4.2. DLQI: Dermatology Life Quality Index

The DLQI is calculated by summing the responses to each of the 10 questions (see Appendix 7 of the protocol) resulting in maximum of 30 and minimum of 0. The higher value of the score denotes higher impairment/lower quality of life.

9.4.3. 5D Itch Scale

The scores of each of the five domains in the questionary (see Appendix 8 of the Protocol) are calculated separately and then summed together to obtain a total 5-D score. 5-D scores can potentially range between 5 (no pruritus) and 25 (most severe pruritus).

Single-item domain scores (duration, degree and direction) are equal to the value indicated below the response choice (range 1–5). The disability domain includes four items that assess the impact of itching on daily activities: sleep, leisure/social activities, housework/errands and work/school. The score for the disability domain is calculated by taking the highest score on any of the four items.

For the distribution domain, the number of affected body parts is tallied (potential sum 0-16) and the sum is sorted into five scoring bins: sum of 0-2 = score of 1, sum of 3-5 = score of 2, sum of 6-10 = score of 3, sum of 11-13 = score of 4, and sum of 14-16 = score of 5.

9.4.4. PhGA: Physician Global Assessment

The score is a subjective assessment of the severity of disease by the physician. The physician uses the visual analog scales and puts a mark on 0-10 cm scale where higher score indicates worse status.

9.4.5. PtGA: Patient Global Assessment

The score is a subjective assessment of the severity of disease by the patient. The patient uses a visual analog scales and puts a mark on the scale where higher score indicates worse status (see Appendix 13 of the protocol).

9.4.6. HAQ-DI: Health Assessment Questionnaire and Disease Index

The HAQ-DI contains eight sections (including dressing & grooming, arising, eating, walking, hygiene, grip, reach, and activities). Each section has multiple questions that the participant can use to rank their functionality (see Appendix 12 of the protocol). For each participant, the average ranking will be reported for each of the eight sections.

The HAQ-DI also contains sections where the participant can indicate use of aids or devices or help from another person from a list of choices.

The HAQ-DI also includes a VAS that the participant can use to indicate the severity of their pain, where a higher score indicates more pain.

9.4.8. EQ-5D-5L & EQ-VAS

The EQ-5D-5L contains five sections, including mobility, self-care, usual activities, pain/discomfort, and anxiety/depression (see Appendix 10 of the protocol). Each of the five sections will be summarized by the number of checked boxes under their respective headers.

The EQ-VAS ranges from 0 to 100, where 100 is the best (ie, most healthful) score.

9.4.9. FACIT-F

The FACIT-F contains 13 questions with ranked scores (see Appendix 11 of the protocol). Each patient's average ranked score will be used in reporting.

C-CASA		
Event Code	C-CASA Event	C-SSRS Response
1	Completed suicide	As captured in the safety database
2	Suicide attempt	"Yes" on "Actual Attempt"
3	Preparatory acts towards imminent suicidal behavior	"Yes" on any of the following: "Aborted attempt", or "Interrupted attempt", or
		"Preparatory Acts or Behavior"
4	Suicidal ideation	"Yes" on any of the following: "Wish to be dead", or "Non-Specific Active Suicidal Thoughts", or "Active Suicidal Ideation with Any Methods (Not Plan) without Intent to Act", or "Active Suicidal Ideation with Some Intent to Act, without Specific Plan", or "Active Suicidal Ideation with Specific Plan and Intent"
7	Self-injurious behavior, no	"Yes" on "Has subject engaged in Non-suicidal
	suicidal intent	Self-Injurious Behavior?"

9.6. Examples of SAS Code for the LANCOVA and ANCOVA Analyses

Create data set ds where for each subject and each visit the following information is stored in the row of the data set.

Table 7. Input Parameters for LANCOVA and ANCOVA Analyses

Id	Subject's id
Cfb	Change from baseline
Time	time of interest (treated as a class variable). Only the post-baseline visits are included
Trt	Treatment group (stored as a class variable, trt="Active" denotes active treatment and "Control" denotes control treatment)
Base	Baseline observation of the outcome

The analysis will be implemented as follows. In all of the LANCOVA and ANCOVA analyses we use the reference baseline value XXX (see below) which is the mean of the baseline values for all participants.

%let basemean=XXX;

LANCOVA-P

The resulting estimates of the visit-dependent difference in means of cfb (active-control treatments) and means of cfb for active and control groups are stored in the dlancovaP and dlancovaMP data sets.

LANCOVA-S

The only difference between the LANCOVA-S and LANCOVA-P analyses is the addition of the time*base term to the model.

The resulting estimates of the visit-dependent difference in means of cfb (active-control treatments) and means of cfb for active and control groups are stored in the dlancovaS and dlancovaMS data sets.

ANCOVA

Create data set ds as described in the Table 7 and sort it by visit. The analysis will be implemented as follows

```
proc mixed data=ds;
by visit;
class id trt (ref="Control") visit;
model cbaseline = trt baseline /ddfm=kr;
lsmeans trt / at baseline = &basemean alpha=0.10 cl pdiff;
ods output diffs= dancovaS lsmeans= dancovaMS;
run;
```

The resulting estimates of the visit-dependent difference in means of cfb (active-control treatments) and means of cfb for active and control groups are stored in the dancovaS and dancovaMS data sets.

9.7. Categories for ECG and Vital Sign Outcomes

The following Pfizer's standard will be used. For the sitting measurements of pulse rate the categories for the supine pulse rate (min <40 bpm and max >120 bpm) will be used.

Categories for QTcF

QTcF (msec)	450≤ max. <480	480≤ max.<500	max. ≥500
QTcF (msec)	30≤ max. <60	max. ≥60	
increase from			
baseline			

Categories for PR and QRS

PR (msec)	max. ≥300	
PR (msec)	Baseline >200	Baseline ≤200 and
increase from	and max.	max. ≥50%
baseline	≥25% increase	increase
QRS (msec)	max. ≥200	
QRS (msec)	Baseline >100	Baseline ≤100 and
increase from	and max.	max. ≥50%
baseline	≥25% increase	increase

Categories for Vital Signs

Systolic BP (mm Hg)	min. <90	
Systolic BP (mm Hg)	max. decrease ≥30	max. increase ≥30
change from baseline		
Diastolic BP (mm Hg)	min. <50	
Diastolic BP (mm Hg)	max. decrease ≥20	max. increase ≥20
change from baseline		
Supine pulse rate (bpm)	min. <40	max. >120
Standing pulse rate (bpm)	min. <40	max. >140

Measurements that fulfill these criteria are to be listed in the study report.

9.8. TIS Calculation in DM

The total improvement score is the sum of all 6 improvement scores associated with the change in each core set measure. A total improvement score of \geq 20 represents minimal improvement, a score of \geq 40 represents moderate improvement, and a score of \geq 60 represents major improvement.

ACR/EULAR CRITERIA FOR CLINICAL RESPONSE IN ADULT DERMATOMYOSITIS AND POLYMYOSITIS

Table 3, Final myositis response criteria for minimal, moderate, and major improvement in adult dermatomyositis/polymyositis (DM/PM) and combined adult DM/PM and juvenile DM clinical trials and studies*

Core set measure, level of improvement based on absolute percent change	Improvement score
Physician global activity	
Worsening to 5% improvement	0
>5% to 15% improvement	7.5
>15% to 25% improvement	15
>25% to 40% improvement	17.5
>40% improvement	20
Patient global activity	
Worsening to 5% improvement	0
>5% to 15% improvement	2.5
>15% to 25% improvement	5
>25% to 40% improvement	7.5
>40% improvement	10
Manual muscle testing	
Worsening to 2% improvement	0
>2% to 10% improvement	10
>10% to 20% improvement	20
>20% to 30% improvement	27.5
>30% improvement	32.5
Health Assessment Questionnaire	
Worsening to 5% improvement	0
>5% to 15% improvement	5
>15% to 25% improvement	7.5
>25% to 40% improvement	7.5 10
>40% improvement	10
Enzyme (most abnormal)	0
Worsening to 5% improvement	
>5% to 15% improvement	2.5 5
>15% to 25% improvement	7.5
>25% to 40% improvement >40% improvement	7.5
Extramuscular activity	13
Worsening to 5% improvement	0
>5% to 15% improvement	7.5
>15% to 25% improvement	12.5
>25% to 40% improvement	15
>40% improvement	20
2-40/c improvement	20

The total improvement score is the sum of all 6 improvement scores associated with the change in each core set measure. A total improvement score of ≥ 20 represents minimal improvement, a score of ≥ 40 represents moderate improvement, and a score of ≥ 60 represents major improvement.

that the criteria for major improvement for adult DM/PM are preliminary.

How to calculate the improvement score: The absolute percent change ([final value – baseline value]) range × 100) is calculated for each core set measure. For muscle enzymes, the most abnormal serum muscle enzyme level at baseline (creatine kinase, aliolase, alianine transaminase, aspartate aminotransferase, lactate dehydrogenase) is used. The enzyme range was calculated based on a 90% range of enzymes from natural history data (34,46), which for creatine kinase is 15 times the upper limit of normal (ULN), for aldolase is 6 times the ULN, and for lactate dehydrogenase, aspartate aminotransferase, and alanine transaminase is 3 times the ULN. The ULN is determined according to the individual laboratories in the participating centers. The ranges for physician global activity, patient global activity, manual muscle testing, Health Assessment Questionnaire, and extramuscular global activity are based on the instrument scale used (3,26). An improvement score is assigned for each core set measure based on the absolute percent change in the core set measure according to the definition. These individual core set measure improvement scores are then totaled among the 6 core set measures to give the total improvement score itself may also be compared among treatment arms in a trial. A total improvement score between 0 and 100 corresponds to the degree of improvement, with higher scores corresponding to a greater degree of improvement.

^{*} Note that these response criteria are also proposed for use in combined adult DM/PM and juvenile DM trials (20). For comparison, the thresholds of improvement in the total improvement score for juvenile DM are ≥30 for minimal improvement, ≥45 for moderate improvement, and ≥70 for major improvement. Also note that the criteria for major improvement for adult DM/PM are preliminary.
